9.6 Statistical Methods

This section describes the statistical methods that address the primary and secondary objectives. Methods related to the exploratory endpoints will be described in the sSAP. No formal hypothesis tests will be conducted for this study.

9.6.1 Statistical Methods for Efficacy Analysis

Efficacy (ORR, DOR, PFS and OS) will be evaluated separately in each cohort, rrcHL and rrPMBCL.

9.6.1.1 Objective Response Rate

The primary efficacy endpoint for this study is the ORR, defined as the proportion of participants who have response (CR or PR) according to Lugano classification as assessed by the investigator. Participants without response data will be considered as nonresponders. The ORR based on BICR will also be provided as supportive.

The point estimate along with 95% exact CI using exact binomial method proposed by [Clopper, J. and Pearson, E. S. 1934] will be calculated.

9.6.1.2 Duration of Response

If sample size permits, DOR will be summarized descriptively using Kaplan-Meier medians and quartiles. Only the subset of participants who show a CR or PR will be included in this analysis. Censoring rules for DOR are summarized in [Table 7](#). DOR analysis will be conducted, separately, for investigator and BICR assessments.

For each DOR analysis, a corresponding summary of the reasons responding participants are censored will also be provided. Responding participants who are alive, have not progressed,

CCI

Table 7

CCI

[REDACTED]	[REDACTED]	[REDACTED]

9.6.1.3

CCI

[figure not shown]
[figure not shown]
[figure not shown]
[figure not shown]
[figure not shown]
[figure not shown]
[figure not shown]

Table 8

CCI

9.6.1.4

CCI

9.6.1.5 Analysis Strategy for Key Efficacy Variables

A summary of the primary analysis strategy for the key efficacy variables is provided in [Table 9](#).

Table 9 Analysis Strategy for Key Efficacy Variables

Endpoint/Variable	Statistical Method	Analysis Population	Missing Data Approach
Primary Analyses			
ORR per Lugano classification by investigator assessment	Summary statistics with 95% CI using exact method based on binomial distribution	APaT	CCI [REDACTED]
Secondary Analyses			
ORR per Lugano classification by BICR assessment	Summary statistics with 95% CI using exact method based on binomial distribution	APaT	CCI [REDACTED]
DOR per Lugano classification by investigator assessment	Summary statistics using Kaplan-Meier method	APaT	CCI [REDACTED]
DOR per Lugano classification by BICR assessment	Summary statistics using Kaplan-Meier method	APaT	CCI [REDACTED]
Exploratory Analyses			
PFS per Lugano classification by investigator assessment	Summary statistics using Kaplan-Meier method	APaT	CCI [REDACTED]
PFS per Lugano classification by BICR assessment	Summary statistics using Kaplan-Meier method	APaT	CCI [REDACTED]
OS	Summary statistics using Kaplan-Meier method	APaT	CCI [REDACTED]
Abbreviations: APaT=all participants as treated; DOR=duration of response; ORR=objective response rate; OS=overall survival; PFS=progression-free survival.			

No formal statistical testing is planned.

9.6.2 Statistical Methods for Safety Analyses

Both cohorts, rrcHL and rrPMBCL, will be pooled for safety evaluations. Safety and tolerability will be assessed by clinical review of all relevant parameters including AEs, laboratory parameters, vital signs, and ECG measurements. The broad AE categories consisting of the percentage of participants with any AE, a drug-related AE, a serious AE, an AE, which is both drug-related and serious, a Grade 3 to 5 AE, a drug-related Grade 3 to 5 AE, and who discontinued due to an AE will be summarized. The number and percentage of participants with increased laboratory toxicity grade shift from baseline will also be provided.

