2 INTRODUCTION

2.1 Study Rationale

On 28-APR-2020, the FDA granted accelerated approval to the additional dosing regimen of 400 mg every Q6W for pembrolizumab across all currently approved adult indications, in addition to 200 mg Q3W dosing regimen. This study is being conducted upon the request of the FDA as a post-marketing requirement to provide additional data on the efficacy and safety of pembrolizumab 400 mg Q6W dosing regimen in participants with rrcHL and rrPMBCL. The results of this study will contribute to an understanding of the safety and efficacy of pembrolizumab administered IV, in a Q6W dosing regimen in the indications rrcHL and rrPMBCL.

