3 HYPOTHESES, OBJECTIVES, AND ENDPOINTS

Hypotheses are aligned with objectives in the Objectives and Endpoints table.

In male and female, programmed cell death 1 protein (PD-1) naïve, participants ≥ 18 years of age with either

- rrcHL who have failed to respond or relapsed after ≥ 1 line of multiagent therapy (can include brentuximab vedotin), or who have failed to achieve a complete response (CR) or relapsed after auto-stem cell transplantation (SCT), or are ineligible for auto-SCT,

OR

- rrPMBCL who have failed to respond or relapsed after ≥ 2 lines of therapy (at least 1 of the prior lines of therapy must contain a rituximab-based regimen), or who have failed to achieve a CR or relapsed after auto-SCT, or are ineligible for auto-SCT:

Primary Objective	Primary Endpoint
To evaluate objective response rate (ORR), by cohort, rrcHL and rrPMBCL, as assessed by the investigator according to Lugano classification criteria [Cheson, B. D., et al 2014] in individuals treated with pembrolizumab Q6W.	Participants with complete response (CR) or partial response (PR).
Secondary Objectives	Secondary Endpoints
To evaluate objective response rate (ORR), by cohort, rrcHL and rrPMBCL, as assessed by blinded independent central review (BICR) according to Lugano classification criteria [Cheson, B. D., et al 2014] in individuals treated with pembrolizumab Q6W.	Participants with complete response CR or PR.
To evaluate duration of response (DOR), by cohort, rrcHL and rrPMBCL, as assessed by the investigator according to Lugano classification criteria [Cheson, B. D., et al 2014] in individuals treated with pembrolizumab Q6W.	The time from first documented evidence of CR or PR until disease progression or death due to any cause, whichever occurs first.

To evaluate duration of response (DOR), by cohort, rrcHL and rrPMBCL, as assessed by BICR according to Lugano classification criteria [Cheson, B. D., et al 2014] in individuals treated with pembrolizumab Q6W.	The time from first documented evidence of CR or PR until disease progression or death due to any cause, whichever occurs first.
To evaluate the pharmacokinetic (PK) profile, immunogenicity of pembrolizumab 400 mg Q6W.	-PK parameters of pembrolizumab including AUC, C _{max} and C _{min} . -Antidrug antibody levels.
To evaluate the safety and tolerability of pembrolizumab Q6W.	-Adverse Events (AEs). -Discontinuations due to AEs.
Tertiary/Exploratory Objectives	Tertiary/Exploratory Endpoints
CCI	[REDACTED]

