9.5.2 Safety Analysis Population

The APaT population will be used for the analysis of safety data in this study. The APaT population consists of all allocated subjects who received at least 1 dose of study treatment.

At least 1 laboratory, vital sign, or ECG measurement obtained after at least 1 dose of study treatment is required for inclusion in the analysis of each specific parameter. To assess change from baseline, a baseline measurement is also required.

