9.9 Sample Size and Power Calculations

A total of 60 participants with rrPMBCL or rrcHL are expected to be enrolled. There is no required minimum enrollment for either cohort. There are no formal hypotheses to be tested. Based on the objectives and the estimated enrollment rates, along with a range of anticipated effect sizes and associated 95% CIs (refer to [Table 10](#) and [Table 11](#)) a sample size of 60 was chosen.

rrPMBCL: Due to rarity of the disease, low enrollment is anticipated for rrPMBCL. [Table 10](#) provides the two-sided 95% exact CIs for ORR for a range of observed response rates (20%, 40% and 60%) for different sample sizes.

Table 10

rrcHL: Table 11 shows the two-sided 95% exact CIs for ORR for a range of observed response rates (20%, 40% and 60%) for different sample sizes.

Table 11

CCP

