9.11 Compliance (Medication Adherence)

9.12 Extent of Exposure

Extent of exposure for a participant is defined as the number of cycles and number of days for which the participant receives the study treatment. Summary statistics will be provided on the extent of exposure for the overall study treatment, by cohort, for the APaT population.

CCI

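### The visible plan summarises safety only with the two cohorts pooled; add rrcHL and rrPMBCL columns beside the pooled one

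*Combined protocol and SAP*

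**What the plan says.** Section 9.6.2 opens its safety methods with "Both cohorts, rrcHL and rrPMBCL, will be pooled for safety evaluations". It then lists what will be tabulated: broad adverse event categories (any, drug-related, serious, Grade 3 to 5, leading to discontinuation, and combinations of these) and laboratory grade shifts. It gives no exception for a display by cohort.

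Three neighbouring parts of the plan keep the cohorts in view:

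- Section 2.1 says the trial is a post-marketing requirement "to provide additional data on the efficacy and safety of pembrolizumab 400 mg Q6W dosing regimen in participants with rrcHL and rrPMBCL", and that its results will inform the "safety and efficacy of pembrolizumab administered IV, in a Q6W dosing regimen in the indications rrcHL and rrPMBCL".
- Section 9.6.1: "Efficacy (ORR, DOR, PFS and OS) will be evaluated separately in each cohort, rrcHL and rrPMBCL".
- Section 9.12: "Summary statistics will be provided on the extent of exposure for the overall study treatment, by cohort, for the APaT population".

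The safety objective in Section 3 (repeated in the synopsis) is worded without a cohort split: "To evaluate the safety and tolerability of pembrolizumab Q6W". The ORR and DOR objectives, by contrast, are stated by cohort.

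On numbers, Section 9.9 says "A total of 60 participants with rrPMBCL or rrcHL are expected to be enrolled", sets no minimum for either cohort, and expects low rrPMBCL enrolment because the disease is rare.

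**The concern.** The trial has two indications to inform. For each, the planned output gives a response rate and an exposure summary, but the visible plan gives no adverse event rate to read beside them. A pooled rate is weighted by cohort size, so if rrPMBCL enrolment is as low as the sponsor expects, it is driven by rrcHL. A reader wanting rrPMBCL safety would have to take the pooled figure on trust, or wait for a split made after the results are known.

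Entry criteria also differ between the cohorts. Section 5.1 asks for at least two prior lines, one of them rituximab-based, on the transplant-ineligible rrPMBCL route, while rrcHL participants can enter after one multiagent line. This does not show that adverse event rates differ. It does mean that equal rates are an assumption, and the plan neither states nor argues for it.

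**Working it through.** **Inputs from the documents.** Total N = 60 (9.9). The safety set is all allocated and treated participants (9.5.2: "The APaT population will be used for the analysis of safety data in this study"). The summaries are descriptive, with no tests (9.1, 9.6). Tables 10 and 11 are blacked out and no expected cohort size is visible, so the plan has no figure to reproduce here.

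**Assumptions.** rrPMBCL n of 5, 10, 15, 20 or 30 out of 60, and true event rates of 20% (rrcHL) and 40% (rrPMBCL). None of these comes from the documents. They only show how pooling behaves.

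**Step 1: the pooled rate.** With m rrPMBCL participants, pooled rate = [(60 − m) × 0.20 + m × 0.40] / 60. Equivalently, the pooled rate exceeds the rrcHL rate by (m/60) × 20 percentage points.

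| rrcHL / rrPMBCL | Expected events | Pooled rate |
|---|---|---|
| 55 / 5 | 11 + 2 = 13 | 13/60 = 21.7% |
| 50 / 10 | 10 + 4 = 14 | 14/60 = 23.3% |
| 45 / 15 | 9 + 6 = 15 | 15/60 = 25.0% |
| 40 / 20 | 8 + 8 = 16 | 16/60 = 26.7% |
| 30 / 30 | 6 + 12 = 18 | 18/60 = 30.0% |

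With 10 rrPMBCL participants, a doubled rate in that cohort moves the pooled figure by 10/60 × 20 = 3.3 points. With equal cohorts it moves by 10 points. The masking is therefore strongest at low rrPMBCL enrolment, which is what the sponsor anticipates, and weakens as the cohorts even out.

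**Step 2: what a cohort column would show.** At 50/10 the table would read 10/50 (20%), 4/10 (40%) and 14/60 (23.3%). The exact (Clopper-Pearson) 95% intervals are 12.2% to 73.8% for 4/10 and 13.4% to 36.0% for 14/60. The plan does not call for intervals on safety rates; these are computed here only to show precision.

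**Step 3: the limits of a small cohort column.** With zero events in n participants, the upper exact 95% limit is 1 − 0.025^(1/n). The chance of seeing at least one case of an event with a true rate of 5% is 1 − 0.95^n.

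| n | Upper limit at zero events | Chance of at least one case at 5% |
|---|---|---|
| 5 | 52.2% | 22.6% |
| 10 | 30.8% | 40.1% |
| 15 | 21.8% | 53.7% |
| 20 | 16.8% | 64.2% |
| 30 | 11.6% | 78.5% |
| 60 (pooled) | 6.0% | 95.4% |

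The pooled column is clearly better for uncommon events. The cohort columns add something different: they show whether the pooled rate represents both cohorts.

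**The case against.** The case for pooling is a fair one. There is one arm, one drug and one fixed dose. Section 4.3 expects the safety profile to be comparable to the established one. The safety objective carries no cohort split, so 9.6.2 follows it, and the contrast with efficacy mirrors the wording of the objectives. Nothing in the documents suggests that safety differs between the cohorts. With few rrPMBCL participants, the pooled estimate is the more precise one, and extra columns cannot cure a small n. All of this stands, and it is why pooling should remain the main summary.

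It does not argue against showing the columns. The plan already reports rrPMBCL ORR with exact intervals while expecting low enrolment, and in 9.6.1.2 it makes the DOR summary conditional on sample size rather than pooling the cohorts. Imprecision is handled by displaying n.

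A reader might infer four stronger things that the documents do not support:

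- **That the trial cannot describe rrPMBCL safety.** Cohort is fixed at allocation, every treated participant is in the safety set, and adverse events are monitored in all. The gap is in the planned tables, not in the data.
- **That no safety display by cohort exists anywhere.** The body of 9.10, listed in the contents as subgroup analyses, is blacked out, as is most of the safety assessment text in Section 8. The point holds for the visible text.
- **That pooling contradicts the safety objective.** It does not; it falls short of the rationale in 2.1.
- **That a signal in rrPMBCL would go unnoticed, or that no benefit/risk view by indication is possible.** Section 9.6.2 also provides for clinical review of adverse events, laboratory values, vital signs and ECGs, and the dilution figures depend on assumed splits and rates.

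**Conclusion.** The point holds as a gap in planned reporting. In the visible plan, safety is the one main domain without a by-cohort summary, although the study is meant to inform safety in both indications. On assumed rates of 20% and 40%, the pooled figure lies between 21.7% and 30.0% for rrPMBCL n of 5 to 30, so it is close to the rrcHL rate only when rrPMBCL is small. That is the situation the sponsor anticipates, but no cohort size is visible to confirm it. The conclusion rests on the blacked-out parts containing no by-cohort safety display. It concerns descriptive output only: the primary analysis, the estimates of ORR and DOR, and the sample size are untouched. It is a cheap improvement, not a defect that threatens the trial.

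**What to change.** Replace the pooling sentence in 9.6.2 with: *Safety will be summarised by cohort and overall (both cohorts combined) for the APaT population.* Show the listed adverse event categories and the laboratory grade shifts in three columns (rrcHL, rrPMBCL, total), each headed by its n. Keep the total column as the main summary, particularly for uncommon events. Add a sentence saying that rrPMBCL estimates will be imprecise and are descriptive.

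If the protocol is not to be amended, the sSAP is the place that Section 9 provides for such changes. Specifying the split there, before the results are seen, keeps it from being a post hoc analysis.

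The cost is one or two sentences and two extra table columns. No new data, visits or participants are needed. The drawback is a sparse rrPMBCL column that could be over-read, which the displayed n and the statement on imprecision address.

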9.6.3 Demographic and Baseline Characteristics

The number and percentage of participants screened and allocated and the primary reasons for screening failure and discontinuation will be displayed. Demographic variables, baseline characteristics, primary and secondary diagnoses, and prior and concomitant therapies will be summarized by descriptive statistics or categorical tables.

9.7 Interim Analyses

No interim analyses are planned for this study.

9.8 Multiplicity

No multiplicity adjustment is required because there is no hypothesis testing.

9.9 Sample Size and Power Calculations

A total of 60 participants with rrPMBCL or rrcHL are expected to be enrolled. There is no required minimum enrollment for either cohort. There are no formal hypotheses to be tested. Based on the objectives and the estimated enrollment rates, along with a range of anticipated effect sizes and associated 95% CIs (refer to [Table 10](#) and [Table 11](#)) a sample size of 60 was chosen.

rrPMBCL: Due to rarity of the disease, low enrollment is anticipated for rrPMBCL. [Table 10](#) provides the two-sided 95% exact CIs for ORR for a range of observed response rates (20%, 40% and 60%) for different sample sizes.

Table 10

rrcHL: Table 11 shows the two-sided 95% exact CIs for ORR for a range of observed response rates (20%, 40% and 60%) for different sample sizes.

Table 11

CCP

9.10 CCI

11. **What is the primary purpose of the *Journal of Clinical Endocrinology and Metabolism*?**

A vertical stack of five black rectangular bars of varying widths, with a thick vertical bar on the far left.

9.11 Compliance (Medication Adherence)

9.12 Extent of Exposure

Extent of exposure for a participant is defined as the number of cycles and number of days for which the participant receives the study treatment. Summary statistics will be provided on the extent of exposure for the overall study treatment, by cohort, for the APaT population.

CCI

